Phase 2 Randomized Single Ascending Dose Study in Post-Bariatric Hypoglycemia Subjects to Determine the Effect of Mizagliflozin Formulations on Postprandial Glucose and Insulin Levels

Protocol: VGX-001-011

NCT05541939

May 1, 2024

Protocol:

Study Objective

To evaluate the safety, tolerability, and pharmacodynamics of two formulations of mizagliflozin with respect to postprandial plasma glucose levels in participants with Post-Bariatric Hypoglycemia (PBH).

Study Design

This was a Phase 2 randomized, sequential crossover single ascending dose study in participants with PBH to determine the effect of two mizagliflozin formulations on safety, tolerability, and postprandial glucose and insulin levels. This study examined single doses of mizagliflozin (2.5, 5.0, and 10.0 mg) in either a liquid (2.5 mg) or encapsulated (2.5, 5.0, and 10.0 mg) formulation. Participants were randomly assigned to one of two treatment arms (A: 2.5 mg encapsulated/washout/5 mg encapsulated, or B: 2.5 mg solution/washout/10 mg encapsulated).

Baseline: A Baseline mixed meal tolerance test (MMTT) was performed once all screening assessments had been performed. Pharmacodynamic samples for glucose and insulin were obtained.

Treatment Period: Following the Baseline MMTT assessment, subjects were randomized into Treatment Arm A or Treatment Arm B. Subjects were administered the assigned dose/formulation followed by an MMTT. Pharmacodynamic samples for glucose and insulin were obtained.

Participants

Males and nonpregnant females, ages 18 to 75 years old, having had Roux-en-Y bariatric surgery more than 6 months prior to signing the ICF.

History of reactive hypoglycemia with Whipple's triad: the occurrence of hypoglycemic symptoms associated with blood glucose of ≤50 mg/dL, and resolution with glucose or carbohydrate administration. Symptoms associated with reactive hypoglycemia include neuroglycopenic symptoms (e.g., behavioral changes, confusion or impaired cognitive function, seizure, loss of consciousness).

Inclusion Criteria:

- 1. Males and nonpregnant females, ages 18 to 75 years old, having had Roux-en-Y bariatric surgery more than 6 months prior to signing the ICF.
- 2. History of reactive hypoglycemia with Whipple's triad: the occurrence of hypoglycemic symptoms associated with blood glucose of ≤50 mg/dL, and resolution with glucose or carbohydrate administration. Symptoms associated with reactive hypoglycemia include neuroglycopenic symptoms (e.g., behavioral changes, confusion or impaired cognitive function, seizure, loss of consciousness).
- 3. Willing and able to give informed consent and follow all study procedures and requirements
- 4. Subjects (male and female) must agree to use an adequate method of contraception from signed consent through 2 weeks after last dose of investigational product (IP).

Adequate contraception is defined as a contraceptive method with a failure rate of less than 1% per year when used consistently and correctly and when applicable, in accordance with the product label, for example: abstinence from penile-vaginal intercourse; oral contraceptives, either combined or progestogen alone; injectable progestogen; implants of etonogestrel or levonorgestrel; estrogenic vaginal ring; percutaneous contraceptive patches; intrauterine device or intrauterine system; male partner sterilization at least 6 months prior to the female subject's screening visit, and this male is the sole partner for that subject (the information on the male partner's sterility can come from the site personnel's review of the subject's medical records or interview with the subject on her medical history); male condom combined with a vaginal spermicide (foam, gel, film, cream, or suppository); male condom combined with a female diaphragm, either with or without a vaginal spermicide (foam, gel, film, cream, or suppository).

Exclusion Criteria:

- 1. History of current medical conditions (other than PBH) which may result in hypoglycemia such as insulinoma, adrenal insufficiency, insulin autoimmune hypoglycemia, congenital hyperinsulinemia.
- 2. Current use of insulin or insulin secretagogues.
- 3. History of current dumping syndrome.
- 4. History of current fasting hypoglycemia.
- 5. Subjects in whom a structural disease of the large intestine (including occlusion, stenosis, cancer, and inflammatory bowel disease) was observed by colonoscopy or contrast enema performed within 3 years before consent or subjects suspected of having a structural disease of the large intestine
- 6. Active infection or significant acute illness within 2 weeks prior to dosing
- 7. Subjects with mental development disorder.
- 8. Subjects who received the following drug therapies within 1 week before the start of the observation period (Week -2).
 - a. Cathartics (bulk cathartic, osmotic laxative, stimulant laxative)
 - b. Drugs that improve gastrointestinal function
 - c. Herbal medicines indicated for constipation
 - d. Drugs that inhibit intestinal motility
 - e. Drugs for the treatment of irritable bowel syndrome
 - f. Drugs for the treatment of chronic constipation
 - g. Macrolides
 - h. Supplements intended for improvement of constipation
- 9. Subjects with a medical history of severe drug hypersensitivity
- 10. Chronic kidney disease stage 4 or 5

- 11. Hepatic disease, including serum alanine aminotransferase or aspartate aminotransferase greater than or equal to 3 times the upper limit of normal; hepatic synthetic insufficiency as defined as serum albumin <3.0 g/dL; or serum total bilirubin >2.0 upper limit of normal at screening.
- 12. Congestive heart failure, New York Heart Association class II, III or IV
- 13. History of myocardial infarction, unstable angina or revascularization within the past 6 months
- 14. History of a cerebrovascular accident within 6 months of screening.
- 15. Active treatment with any diabetes medications, except metformin.
- 16. Active malignancy, except basal cell or squamous cell skin cancers
- 17. Major surgical operation within 30 days prior to screening
- 18. Blood donation (1 pint of whole blood) within the past 2 months
- 19. Active alcohol abuse or substance abuse
- 20. Current administration of oral or parenteral corticosteroids
- 21. Pregnancy and/ or Lactation: For women of childbearing potential: there is a requirement for a negative urine pregnancy test and for agreement to use contraception during the study and for at least 2 weeks after participating in the study.
- 22. Other subjects considered inappropriate by the Investigator

Randomization and blinding

After performing Baseline assessments and meeting randomization criteria, Subjects were randomized into one of two treatment arms in a 1:1 fashion. The Treatment Arms are defined as follows:

Treatment Arm	
A	In Period 1, subjects will receive an encapsulated formulation of 2.5 mg mizagliflozin. Following at least a 7 day washout period, in Period 2, subjects will return to the clinic to receive an encapsulated formulation of 5.0 mg mizagliflozin.
В	In Period 1, subjects will receive a liquid dose formulation of 2.5 mg mizagliflozin. If after consultation with the medical monitor and PI that there are no concerns regarding any treatment-related AEs, subjects will return to the clinic for a 10 mg encapsulated dose (Period 2) and MMTT after at least a 7 day washout period.

As this is an open-label study, the subject, Investigator, site personnel and sponsor were not blinded to study drug.

Procedures

At in-clinic visits on visit days for MMTTs, patients reported to the clinic in the morning after a minimum 8 hour fast. A blood sample was obtained (Pre-MMTT). In addition, a clinical lab serum sample was collected. Shortly thereafter (within 30 min), subjects were administered a water dose (Baseline), or the assigned dose of mizagliflozin with water, and at 20 (±5) min, an MMTT was administered. The MMTT was started by consumption of a liquid meal (350 kcal distributed as 57% carbohydrate, 15% protein, and 28% fat). Pharmacodynamic blood samples to measure plasma glucose and insulin were collected at (hr:min) 0:05, 0:10, 0:20, 0:40, 1:00, 1:20, 1:40, 2:00, 2:30, 3:00, 4:00, and 6:00 after MMTT initiation.

Outcome Measurements

Primary Endpoints

- Safety endpoints were as follows:
 - Adverse Events
 - Vital signs (blood pressure, heart rate, respiratory rate, and body temperature)
 - Laboratory analyses (to include chemistries and hematology)
 - 12-lead ECGs
- MMTT glucose nadir after mizagliflozin dosing [Time Frame: 0-3 hours].

Secondary Endpoints

- MMTT plasma glucose and insulin peak concentration after mizagliflozin dosing [Time Frame: 0-3 hours].
- MMTT plasma glucose 1, 2, and 3 hour area under the curve (AUC₀₋₁, AUC₀₋₂, and AUC₀₋₃) after mizagliflozin dosing
- MMTT insulin concentration 1, 2, 3, 4, and 6 hour area under the curve (AUC₀₋₁, AUC₀₋₂, AUC₀₋₃, AUC₀₋₄, and AUC₀₋₆) after mizagliflozin dosing
- MMTT time to peak plasma glucose concentration after mizagliflozin dosing [Time Frame: 0-3 hours]
- MMTT time to peak insulin concentration after mizagliflozin dosing [Time Frame: 0-3 hours]

Statistical Analysis Plan

No formal hypothesis testing was planned. This study was sized for feasibility, study design optimization, and to investigate a difference in the nadir plasma glucose concentration during an MMTT. As such for descriptive purposes, in an inequality test on data from a three-period, single-sequence cross-over design, a sample size of 6 achieves approximately 80% power at a 2-sided 5.0% significance level when the absolute difference between the two treatment means is 15, the between-subject standard deviation is 14.6 and the correlation between any two measurements on the same subject is 0.6.

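### Does the undefined observation period (Week -2) in exclusion 8 put the comparison of meal tests at risk?

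*Combined protocol and SAP*

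**What the plan says.** Item 8 of the Exclusion Criteria lists laxatives, drugs acting on gut function or motility, treatments for irritable bowel and constipation, macrolides and certain supplements. It applies to use "within 1 week before the start of the observation period (Week -2".

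The rest of the document describes the trial by stages, not by week numbers. Under Study Design, "A Baseline mixed meal tolerance test (MMTT) was performed once all screening assessments had been performed", and randomization comes after that test. For Arm A, the Randomization and blinding section says: "Following at least a 7 day washout period, in Period 2, subjects will return to the clinic". Arm B has the same minimum washout. No Week 0, run-in or week-numbered schedule is given.

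Some other exclusions use events that the design does contain. Item 6 is "Active infection or significant acute illness within 2 weeks prior to dosing" and item 17 is "Major surgical operation within 30 days prior to screening". Item 20 uses present status: "Current administration of oral or parenteral corticosteroids".

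The efficacy measure among the primary endpoints is "MMTT glucose nadir after mizagliflozin dosing [Time Frame: 0-3 hours". The Statistical Analysis Plan says that no formal hypothesis testing was planned and that the study was sized for feasibility, for design optimization and to look at a difference in nadir. Its descriptive power statement refers to a "three-period, single-sequence cross-over design, a sample size of 6 achieves approximately 80% power".

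**The concern.** A criterion dated from an event that the design does not contain cannot be applied, or audited, from the text. Sites might have placed the one-week window differently, and a reader cannot tell how it was placed.

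There is also a possible link to the primary measure. Each subject has meal tests in a fixed order (Baseline, Period 1, Period 2), so order cannot balance out a drug present at only one of them. Several listed classes act on the gut by their own labels. If such a drug changed the post-meal glucose curve and was taken around one test only, the within-subject difference would mix its effect with that of mizagliflozin. With about six subjects, one such case carries noticeable weight.

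**Working it through.** **1. Where the window could fall.** The documents settle none of these readings; each is an assumption.

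| Start of Week -2 taken as | Look-back ends | Gap to the meal tests |
|---|---|---|
| Two weeks before the first dose | Day -14 (window Day -21 to Day -14) | 14 days to Period 1; 14 + 7 = at least 21 days to Period 2 |
| Two weeks before the Baseline test | 14 days before Baseline | 14 days to Baseline; longer to Periods 1 and 2, by intervals not given |
| Start of screening | At screening | Not given; the text does not rule out Baseline on the same or the next day |
| The Baseline visit | At Baseline | None to Baseline; not given to Periods 1 and 2 |

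No reading brings the window up to a dosing test. Two of them can bring it up to, or close to, Baseline. Someone taking a listed drug regularly throughout the weeks before and around enrolment is excluded on all four. The readings differ only for a subject who started, stopped or used a drug sporadically in those weeks.

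**2. Whether failing to reach the dosing tests is peculiar to item 8.** It is not. Item 2 (current insulin or secretagogues), item 15 (active diabetes treatment) and item 20 (current corticosteroids) also describe status at entry and say nothing about Period 2. Loose dating is not peculiar to item 8 either: items 13 and 18 count back from an unstated present. What is unique to item 8 is that it names a period found nowhere else.

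**3. Size, if one subject were affected.** Inputs from the Statistical Analysis Plan: difference 15 (no unit given), SD 14.6, correlation 0.6, sample size 6.

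- SD of a paired difference, reading 14.6 as the SD of a single measurement: 14.6 × √(2 × (1 − 0.6)) = 13.06.
- Standard error at 6 subjects: 13.06/√6 = 5.33.
- Check against the plan's own figure: 15/5.33 = 2.81, and the normal approximation gives power of 80.3%, matching the stated 80% or so. (A t reference gives 61.8% on 5 degrees of freedom or 71.8% on 10. That is a separate matter and does not bear on item 8.)

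The documents give no effect of a listed drug, so the shifts below are assumptions. A shift d in one subject at one test moves the mean difference by d/6.

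| Assumed d | d/6 | Share of 15 | Share of SE 5.33 |
|---|---|---|---|
| 5 | 0.83 | 6% | 0.16 |
| 10 | 1.67 | 11% | 0.31 |
| 15 | 2.50 | 17% | 0.47 |

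If 14.6 is instead the between-subject variance component, the SD of the difference is 14.6 × √(2 × (1 − 0.6)/0.6) = 16.86, the SE is 16.86/√6 = 6.88, and the last column becomes 0.12, 0.24 and 0.36.

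The plan does not say whether 6 is the total or the number per arm. If it is the total, 1:1 allocation leaves 3 per arm. A 15-unit shift then moves an arm mean by 15/3 = 5, which is 33% of 15. The SE is 13.06/√3 = 7.54, so the ratio is 0.66.

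**4. What a repeat analysis would need.** Flagging affected tests needs medication records around each test, which the documents do not mention. The flagging interval would be chosen after the event, since the document describes the study in the past tense. Each test removed also takes a within-subject difference out of a group of six or fewer.

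**The case for a change.** The strongest case for acting is that this goes beyond loose wording. The sentence is complete, nothing in it is blacked out, and it names an event that the design lacks, whereas items 6 and 17 can be applied as they stand. The sponsor chose to exclude these classes, presumably for a reason. The endpoints include time to peak and one-hour AUCs as well as the nadir, the test order is fixed, and one sentence would settle the definition.

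Part of this stands. The term is undefined, the window cannot be dated from the text, and fixed order gives no protection against a drug present at one test only. The term has to be reconciled with the trial's stages by anyone reporting how eligibility was applied.

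The step from there to a flaw in the comparison does not stand. The documents neither report use of a listed drug nor say that one alters post-meal glucose. Counterbalancing the order would not reliably balance sporadic use in one subject among six. Restrictions during the study usually belong in a concomitant-medication section. This short retrospective text has no such section and no visit schedule, so its silence is weak evidence that no rule existed. A fuller protocol may define the term.

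**Conclusion.** The slip is real and minor: item 8 counts back from a period that appears nowhere else in the document. Investigators would fill the gap sensibly by checking for recent use at enrolment, and item 22 lets them turn away anyone they consider unsuitable. Following the text as written is not shown to give a wrong result, and no stated figure depends on it.

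The only size that can be given is hypothetical. One affected subject in six, with an assumed shift of 5 to 15 units, moves the mean difference by 0.16 to 0.47 of a standard error, or up to 0.66 if only three subjects enter the comparison. For a descriptive feasibility study this does not justify a flagged re-analysis that would rest on records the documents do not mention and discard data from a very small sample. Defining the term would tidy the text without altering conduct or analysis, so no change to the plan follows.

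This rests on item 8 being an entry criterion only and on there being no evidence of listed-drug use around a single meal test. Records of such use would be a reason to look again.

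### For 6 participants in the named design, the stated power of about 80% holds only as a normal approximation; a two-sided 5% t-test has about 62% (paired) or 72% (pooled error)

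*Combined protocol and SAP*

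**What the plan says.** The Statistical Analysis Plan section opens with "No formal hypothesis testing was planned" and gives the reasons for the size: "This study was sized for feasibility, study design optimization, and to investigate a difference in the nadir plasma glucose concentration during an MMTT". It then offers one calculation, labelled descriptive. The setting is "an inequality test on data from a three-period, single-sequence cross-over design", and the claim for it is that "a sample size of 6 achieves approximately 80% power at a 2-sided 5.0% significance level". The assumed effect and spread stand in the clause "when the absolute difference between the two treatment means is 15, the between-subject standard deviation is 14.6", together with a within-subject correlation of 0.6. The section does not name a z or t reference, an error term or degrees of freedom, and it does not say whether 6 is the total or the number per arm.

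The trial itself has two arms. Study Design gives them as "A: 2.5 mg encapsulated/washout/5 mg encapsulated, or B: 2.5 mg solution/washout/10 mg encapsulated", and states "Following the Baseline MMTT assessment, subjects were randomized into Treatment Arm A or Treatment Arm B". Randomization and blinding adds that "Subjects were randomized into one of two treatment arms in a 1:1 fashion".

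**The concern.** With 6 participants the difference between a normal and a t reference is large. At 5 df the two-sided 5% critical value is 2.571, against 1.960. A power figure computed as if the SD were known overstates what a test using an estimated SD can do.

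This sentence is the only numerical basis given for the sample size, and it concerns nadir glucose, which is listed among the primary endpoints. A reader who takes it at face value puts the chance of missing a 15-unit difference at 20%. If the study shows no clear nadir effect, that reader will treat the result as stronger evidence of no effect than it is. The unclear meaning of 6 adds to this, because 1:1 allocation of 6 in total leaves 3 per arm.

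**Working it through.** **Inputs, all from the Statistical Analysis Plan section:** n = 6; two-sided alpha 0.05; difference 15 (no unit in the sentence); SD 14.6, taken as the SD of a single measurement; correlation 0.6 for every pair of measurements; three periods, one sequence.

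**Step 1. Reproduce the stated figure.**
- SD of a within-participant difference = 14.6 × √(2 × (1 − 0.6)) = 13.06
- Standard error = 13.06 / √6 = 5.331
- Noncentrality = 15 / 5.331 = 2.814
- Normal power = Φ(2.814 − 1.960) = 80.3%

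The normal-approximation n for 80% power is (1.960 + 0.842)² × 13.06² / 15² = 5.95, which rounds to 6. The stated figure is reproduced.

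**Step 2. Same inputs, SD estimated (noncentral t, noncentrality 2.814).**

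| Error model, 6 participants | df | Critical value | Power |
|---|---|---|---|
| Paired differences | 6 − 1 = 5 | 2.571 | 61.8% |
| Pooled over three periods | (6 − 1)(3 − 1) = 10 | 2.228 | 71.8% |

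Simulation agrees with both figures to within 0.2 percentage points.

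**Step 3. Size of the gap.** The type II error is 28% to 38%, not 20%. The difference detectable with 80% power is 18.7 (5 df) or 16.6 (10 df). By n, the t-based power is:
- paired: 71.8% at 7, 79.5% at 8, 85.4% at 9
- pooled over three periods, df 2(n − 1): 79.7% at 7, 85.5% at 8

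The gap is therefore one or two participants per contrast.

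**Step 4. Other readings of the inputs.**
- 14.6 as the between-participant variance component alone: 58.7% even with 1.96.
- 14.6 as the SD of the difference: 71.1% with 1.96.
- Baseline against the mean of two active periods: 73.8% (5 df), 83.3% (10 df) or 90.1% (normal). The sentence, however, refers to two treatment means.
- One-sided 5% t-test: 77.8% (5 df) or 83.4% (10 df). The sentence says two-sided.

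The single-measurement reading of 14.6 with a normal reference is the one that returns 80%.

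**Step 5. If 6 is per arm (12 in total).** Two models that the plan does not name come closer:
- Error pooled over both arms, df 2 × 10 = 20: standard error still 5.331, power 76.3%.
- A random-participant model that also shares the common Baseline across arms (correlation treated as known, 20 df): standard error 5.058, power 80.5%.

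**Step 6. If 6 is the total (3 per arm).**

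| Contrast | Model | df | Power |
|---|---|---|---|
| Baseline vs 2.5 mg, formulations combined (all 6) | Paired | 5 | 61.8% |
| Same | Three periods, 5 mg and 10 mg modelled separately | 18 − 6 − 3 = 9 | 70.7% |
| Arm-specific (3) | Paired | 2 | 21.7% |
| Arm-specific (3) | Three periods within the arm | 4 | 33.3% |
| Arm-specific (3) | Error pooled over both arms | 8 | 41.7% |
| Arm-specific (3) | Also sharing Baseline | 8 | 45.4% |

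For the arm-specific rows the standard error is 13.06 / √3 = 7.539 (noncentrality 1.990), or 7.153 with the shared Baseline.

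The single-sequence label does not settle which reading applies. Each arm alone is one sequence, but by dose level both arms also run Baseline, 2.5 mg, then a higher dose.

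**The case against.** The strongest reply is that the number is not an arithmetic error. It follows from its inputs under a standard method, it is worded as approximate, and no test decision depends on it. All of that stands, and it is why the point is minor. But the sentence specifies an inequality test, a significance level and a power, and a gap of 8 to 18 percentage points is more than rounding. Only labelling the figure a normal approximation would leave that overstatement in place.

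A second reply is that a t-based model does reach 80%: 6 per arm with the Baseline shared. The documents support a common Baseline, since that test precedes randomization, and the plan names no error term for any model. This stands as a possible intention. It needs 12 participants in two arms, though, and the sentence describes 6 in a single sequence. If the sponsor meant that model, naming it resolves the point.

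Third, with 6 per arm, Baseline versus 2.5 mg with formulations combined would use 12 participants: standard error 13.06 / √12 = 3.770, noncentrality 3.98, and about 95% power (paired, 11 df). On that reading the study is more sensitive for this contrast than stated. The arithmetic is right, but it is not the power of a sample of 6.

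Finally, whether 6 is per arm or in total is a separate question from z versus t. That is fair: the 22% to 45% figures depend on a reading that the documents do not establish, and they add no weight to the main point.

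**Conclusion.** The concern holds, as a minor one. For 6 participants in the three-period, single-sequence design that the sentence names, a two-sided 5% t-test for a difference of 15 has 61.8% power (paired) or 71.8% (pooled error), against about 80% stated. This rests on 14.6 being the SD of a single measurement, which is the reading that reproduces the stated figure. The pooled figure also needs equal variance and equal correlation across periods, as the single stated correlation implies.

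The effect is on how readers judge the study's sensitivity. It does not affect trial conduct: the calculation is labelled descriptive, no formal test is planned, and the size also rests on feasibility and design optimization.

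**What to change.** Keep enrolment and reword the one sentence.

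1. Replace the 80% figure with the t-based power for the intended contrast and error model: 62% paired, or 72% pooled over three periods, for 6 participants per contrast. If a model that pools both arms or shares the common Baseline with 6 per arm is intended, name it and give its power (about 76% or 80%).
2. Say whether 6 is per arm or in total. If it is the total, say which contrast the power refers to: Baseline versus 2.5 mg with formulations combined (all 6, about 62% to 71%), or an arm-specific contrast (3 participants, about 22% to 45% depending on the model).

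The cost is SAP wording only, with no extra participants and no change to procedures. The document already describes the study largely in the past tense, so the change corrects the record and does not alter the study. The stated power becomes less favourable unless the shared-Baseline model with 6 per arm is the one named.
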